The main known adverse reaction to metformin is lactic acidosis. Metformin associated lactic acidosis (MALA) is exceedingly rare and is manifested as nonspecific symptoms such as malaise, myalgias, abdominal pain, respiratory distress, or increased somnolence. The incidence of MALA is exceedingly rare approximately 0.03 to 0.06 per 1000 patient years (32). In post marketing data analysis, there have been 47 documented MALA events in 1 million users. Metformin-associated lactic acidosis is characterized by elevated blood lactate concentrations (>5 mmol/L), anion gap acidosis (without evidence of ketonuria or ketonemia), and an increased lactate:pyruvate ratio. According to FDA insert, metformin associated lactic acidosis primarily occurs in patients with renal impairment. Thus to minimize the risk of adverse, we have added a safety time point to measure renal function during the course of the study. We will follow guidelines from the FDA which limit initiation of Metformin to patients with GFR's over 45 ml/min*1.73m² (23). If the GFR drops to between 30 and 45 ml/min*1.73m², despite the fact that the FDA allows continuation of metformin until a GFR of 30 ml/min*1.73m² we will dose reduce to 1 gram total per day of study drug as per American Diabetes Association Guidelines(33).

Study drug treatment will be discontinued in the following situations: 1) when subject withdraw consent, 2) in case of pregnancy, 3) when subjects develop severe renal dysfunction (defined as estimated GFR <30 ml/min*1.73 m²), or 4) when subjects develop a condition which, in the investigator's judgment, precludes further therapy (please see Data Safety Monitoring Plan). Temporary discontinuation of the drug will occur if the patient is to undergo a procedure that include iodinated contrast agent that could affect renal function. Discontinuation will have no consequence on regular patient care. There will be no dose modifications of the study medication as there is none indicated by the FDA.

Blood Draw: Phlebotomy is a commonly used medical procedure for screening and follow-up of disease. Efforts to decrease the risks associated with blood draws include using highly experienced staff, applying external pressure to the site of the blood draw for a specified time following the draw, and the use of aseptic technique throughout the procedures. The amount of blood phlebotomized for analysis (20 mL) is not anticipated to be associated with significant risk.

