We plan to collect and store biological samples for later batch analysis. These samples will be stored in the Columbia University, [name] Lab. Subjects will be fully informed regarding the storage and potential future use of their samples during the consent process for the study.

2. List of specific tests that will be done to monitor patient safety

The following tests will be performed to ensure patients' safety:

- a) Serum chemistry (creatinine) and venous lactate on day 0, 30 and 180
- b) Vital Signs on day 30 and 180
- c) Physical Exam on day 180
- d) Adverse Event check at 30 days after endpoint of the trial (after last known dose of either placebo or study drug)

3. What adverse events/toxicities are expected?

Three safety outcomes have been designated:

- a) Worsening renal function: Decline in eGFR to $<45\text{ml}/\text{min} \cdot 1.73\text{m}^2$, day 30
- b) Venous Lactate: Rise in venous lactate level to $\geq 2.0\text{mmol/L}$ on day 30

c) Hypoglycemia defined as a fasting glucose <60mg/dL on day 30

4. What are the serious adverse events?

Serious adverse events have been designated:

- a) Death
- b) Life threatening illness
- c) Congenital Abnormality
- d) Hospitalization
- e) Venous Lactate: Rise in serum lactate $\geq 2\text{mmol/L}$, at any point
- f) Hypoglycemia: Fasting glucose <60mg/dL, at any point

GFR falling below 45ml/min is defined as a safety event because it requires dose adjustment however it is not defined as a serious adverse event.

Specific responses to anticipated possible adverse events are detailed below:

Table 2: Serious Adverse Events

Adverse Event	Action
Death	Discontinuation of study drug. DSMB will unblind the allocation and determine if the death was related to the study drug.
Life threatening illness	Discontinuation of study drug if it is either 1) unsafe to continue for medical reasons by either the treating physicians, the PI of the study, or the DSMB, or 2) if it deemed by the DSMB to be related to the study drug. The DSMB will unblind the allocation and determine if the illness is related to the study drug.

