Congenital Abnormality	Pregnancy is an exclusion criteria for this study and patients will be advised not to become pregnant during this study. However, if we detect a pregnancy that occurs during the study (there is a pregnancy test at the end of study), we will stop the study for that patient. We will mandate that we follow the patient until after birth to determine if there is a congenital abnormality. If we detect this event, the DSMB will be required to unblind the allocation (if the trial is ongoing) and determine if the congenital abnormality is related to the study drug.
Hospitalization	Discontinuation of study drug if it is either 1) unsafe to continue for medical reasons by either the treating physicians, the PI of the study, or the DSMB, or 2) if it deemed by the DSMB to be related to the study drug. The DSMB will unblind the allocation and determine if the hospitalization is related to the study drug.
Venous Lactate rises to $>2\text{mmol/L}$	Discontinue study drug, de-identification of study medication. Repeat lactate daily until normalizes. Contact primary cardiologist. Consider inpatient hospitalization.
Fasting Serum Glucose <60mg/dL	Discontinue current regimen. Administer patient oral glucose. Repeat value until normalizes. Referral to primary physician/cardiologist. Referral to ED if for referral or assessment if symptomatic and non-responsive to glucose tabs.

Renal Impairment for already enrolled patients

Glomerular Filtration Rate	Action
GFR \geq 45ml/min/1.73m ²	No action
GFR 30 - 44ml/min/1.73m ²	Reduce total dosage to 500mg twice a day. Schedule follow up basic metabolic panel in 3 months if GFR measurement occurs >3 months from scheduled end of trial. If follow up GFR is greater than 45 ml/min/1.73m ² , then patient can revert dosage to 2 grams per day. If GFR is less than 30 ml/min/1.73m ² , study drug and patient enrollment will be terminated.
GFR <30ml/min/1.73m ²	Stop Drug and patient enrollment in trial

5. Reporting of adverse events/adverse drug reactions

Adverse events (AEs) will be reported to the IRB and the DSMB. Adverse events will be reported on a weekly basis to the DSMB and serious adverse events will be reported to the IRB and DSMB within 24 hours of being detected.

6. Who will review AEs and other safety data?

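### The risk section denies any dose modification although the plan's own renal rule requires one; separately, the lactate cut-off is ≥2.0 in two places and >2.0 in two others

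*Combined protocol and SAP*

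**What the plan says.** **Dose.** The Study Drug paragraphs of Specific study risks make two statements that do not agree.

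- The first paragraph sets a renal rule. It opens with "If the GFR drops to between 30 and 45" and continues "we will dose reduce to 1 gram total per day of study drug". It notes that the FDA would allow metformin down to a GFR of 30 and follows American Diabetes Association guidance instead.
- The next paragraph, on discontinuation, ends with "There will be no dose modifications of the study medication as there is none indicated by the FDA".

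The Data and Safety Monitoring Plan agrees with the first paragraph. Item 4 says "GFR falling below 45ml/min is defined as a safety event because it requires dose adjustment", without naming a dose. The table headed Renal Impairment for already enrolled patients says, for GFR 30-44, "Reduce total dosage to 500mg twice a day". The same row allows a return to 2 g/day on this condition: "If follow up GFR is greater than 45".

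**Lactate.** Four statements set a limit. Item 3b (day-30 safety outcome) and item 4e (serious adverse event at any time) of the Data and Safety Monitoring Plan use ≥2.0 mmol/L. The serious adverse event definition under Safety Monitoring and the lactate row of Table 2 use >2.0. The Table 2 row stops study drug and requires daily repeat lactates.

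**The concern.** These are working rules for dosing, stopping drug and reporting, so they should give one instruction for each result.

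For a participant whose GFR falls to 30-44, neither keeping the dose nor halving it complies with every sentence. Deviations therefore cannot be judged consistently. The sentence at fault denies the safeguard in the setting that the same section names as the main one for metformin lactic acidosis, namely renal impairment.

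For lactate, the sign decides whether a borderline result goes to the IRB and DSMB within 24 hours as a serious adverse event or is handled in the weekly adverse event report. It also decides whether drug is stopped.

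**Working it through.** The plan states no figure to reproduce here. The check is a comparison of statements, followed by sizing.

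**1. Dose statements side by side**

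| Place | Rule at GFR 30-44 |
|---|---|
| Specific study risks, first Study Drug paragraph | reduce to 1 g/day |
| Specific study risks, next paragraph | no modification |
| Data and Safety Monitoring Plan, item 4 | GFR below 45 needs adjustment, dose not named |
| GFR action table | 500 mg twice a day |

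Three statements require a change and one denies it. The denial rests on there being no FDA-indicated modification, but the preceding paragraph has already chosen to be stricter than the FDA.

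Size if the sentence were followed literally: 2 × 1,000 = 2,000 mg/day, against 2 × 500 = 1,000 mg/day under the table. The ratio is 2.0.

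**2. GFR of exactly 45**

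The action table's first row gives no action at ≥45, and its second row covers 30-44. The risk section's band runs from 30 to 45 and so may include 45. For a participant already on the reduced dose, a follow-up GFR of exactly 45 falls in the no-action row but does not meet the condition for return to 2 g/day, which is strictly above 45.

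**3. Lactate statements side by side**

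| Place | Limit (mmol/L) | At exactly 2.0 |
|---|---|---|
| Item 3b, day-30 safety outcome | ≥2.0 | counts |
| Item 4e, serious adverse event | ≥2 | counts |
| Safety Monitoring, serious adverse event | >2.0 | does not count |
| Table 2, stop-drug row | >2 | no action |

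**4. How often a reading of exactly 2.0 might occur**

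The documents give no lactate distribution. As an assumption, take values as normal and reported to 0.1 mmol/L, with mean 1.0 to 1.6 and SD 0.3 to 0.5. Then P(exactly 2.0) = Φ((2.05 − mean)/SD) − Φ((1.95 − mean)/SD), and the expected number at day 30 is 50 × P.

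| Mean, SD | P | 50 × P |
|---|---|---|
| 1.0, 0.3 | 0.0005 | 0.03 |
| 1.2, 0.4 | 0.0136 | 0.68 |
| 1.4, 0.4 | 0.0325 | 1.62 |
| 1.6, 0.4 (largest in the range) | 0.0605 | 3.02 |

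For scale, at mean 1.6 and SD 0.4 the expected number of readings above 2.0 is 50 × P(value > 2.05) = 50 × 0.130, or about 6.5. Those are serious adverse events and stop drug under either sign.

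**The case against.** The strongest reply on dose is that the rule in force is not in doubt. The reduction is explicit in the preceding paragraph and again in the action table that staff would consult. The denying sentence closes a paragraph about discontinuation and may be leftover text, or may mean no *other* modifications. Most of this stands and limits the practical effect. It does not make the sentence correct, because the sentence carries no such qualification.

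On lactate, the conflict is one sign in text read from PDF, where the bar under a ≥ can be lost. That is possible, so the signs should be checked against the source file. If they are genuine, the conflict still touches only one value. The risk section describes metformin lactic acidosis by "elevated blood lactate concentrations (>5 mmol/L", far above the disputed boundary.

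It can also be said that ≥2.0 is no more correct than >2.0. That is right: either sign removes the conflict, and the choice is a preference.

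Three stronger readings are tempting but not supported.

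- A reader might infer that participants with falling renal function would be left on 2 g/day. The action table says otherwise.
- A reader might take the words "precludes further therapy (please see Data Safety Monitoring Plan" as the plan's own pointer from dosing to the action table. The cross-reference belongs to the fourth reason for stopping drug and says nothing about dosing.
- A reader might infer from the day-90 final visit under Safety Monitoring, and from the short final-visit blood list, that end-of-treatment safety tests are missing. Item 2a of the Data and Safety Monitoring Plan sets creatinine and lactate on days 0, 30 and 180, and Table 1 marks fasting glucose on day 180. These slips, and the g/dL unit for glucose, are clerical and not part of this point.

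**Conclusion.** The point holds as an internal inconsistency with a small practical effect. The sentence denying dose modification is wrong as written. Its cost would be a twofold difference in dose at GFR 30-44, but only if someone followed it in preference to the table.

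The lactate limit differs between sections, and only a reading of exactly 2.0 is affected. The estimate of about 0 to 3 of 50 participants at day 30 rests wholly on the assumed normal distribution and reporting to 0.1 mmol/L. It should be read as an order of magnitude. It also assumes that the signs in the source file are as they appear here.

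The primary endpoint, the analysis and the sample size are unaffected. The wording should still be corrected, because these rules govern dosing, stopping and 24-hour reporting and the repair is very short.

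**What to change.** One short amendment:

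1. In Specific study risks, replace the sentence with *no dose modifications other than the renal reduction in the GFR action table*.
2. Write the risk section's GFR band as 30-44, and let the dose return to 2 g/day at a follow-up GFR of ≥45, so that exactly 45 has one rule for enrolled participants.
3. Choose one lactate sign and use it in item 3b, item 4e, Safety Monitoring and the Table 2 row. With ≥2.0, the cautious choice, slightly more participants would stop drug: those reading exactly 2.0, about 0 to 3 of 50 at day 30 under the assumption above. With >2.0, the current stop rule is unchanged and the serious adverse event list narrows by that one value.

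The clerical slips can be corrected in the same amendment. There are no new visits, and no change to endpoints, analysis or sample size. Apart from the amendment itself, the only cost is the extra stopping if ≥2.0 is chosen; at day 180 treatment is ending anyway.

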Patients will be randomized to either metformin or placebo. Metformin dose will begin with 500mg twice a day for the first two weeks and then increase to 1000mg twice a day for the remainder of the trial. In order to minimize GI side effects, the medication will be taken with a meal. The intervention will last 180 days. Prior to randomization all potential study subjects will be evaluated with complete medical history and brief physical examination, complete review of home medications, measurement of vital signs and body weight with calibrated scale, serum collection for basic metabolic panel, hemoglobin A1c and liver function test. All patients will also undergo cardiopulmonary exercise testing and transthoracic echocardiography. Patients who meet all the inclusion criteria will be required to complete the informed consent form. Patients will have 2 office visits in total, one at day 1 (baseline) and one on day 180 (final). On day 30, participants will have a blood work for basic metabolic panel, venous lactate and fasting plasma glucose for adverse event assessment (safety). On the final visit, patients will undergo repeat echo, labs and cardiopulmonary exercise testing. The timing of all procedures in this study is outlined in the table 1. Procedural timeline and further details of the relevant procedures are as follows:

Medical history and physical exam: Subjects will be asked to provide information about their basic demographics: age, gender, and race as well as previous and current health and medications. The subject will have his or her height, weight, blood pressure both supine and standing, heart rate, respiratory rate and body temperature recorded. A HF-focused physical examination will be performed and recorded. A Minnesota Living with Heart Failure Questionnaire will be completed.

Blood tests:

Blood be drawn via venipuncture. The following will be prospectively measured for every patient at the indicated time points.

- Screening: fasting insulin and glucose level, basic metabolic, liver function test and HgbA1c
- Baseline: , BNP, venous lactate
- Safety: basic metabolic panel, venous lactate and fasting glucose
- Final: basic metabolic panel, BNP

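### The designated renal safety outcome counts eGFR below 45 at day 30 only, although the same plan calls such a fall a safety event without a day limit and schedules creatinine at day 180

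*Combined protocol and SAP*

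**What the plan says.** Item 3 of the Data and Safety Monitoring Plan opens "Three safety outcomes have been designated". The renal one begins "Worsening renal function: Decline in eGFR to", gives a threshold of 45 ml/min per 1.73 m² and ends with day 30. The lactate outcome carries the same day. The third reads "Hypoglycemia defined as a fasting glucose <60mg/dL on day 30".

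Item 4 lists the serious adverse events. Raised lactate and low fasting glucose appear there with no time limit. The sentence after the list calls a GFR below 45 a safety event, attaches no day to it, and adds "however it is not defined as a serious adverse event".

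Item 2 of the same plan schedules "Serum chemistry (creatinine) and venous lactate on day 0, 30 and 180". Study Intervention and Procedures states "The intervention will last 180 days", and the dose goes up after two weeks: "then increase to 1000mg twice a day for the remainder of the trial".

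The Statistical Approach specifies no between-arm analysis of safety. The only safety analysis mentioned is one that the DSMB may request (item 8).

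**The concern.** One event, eGFR falling below 45, has two definitions within a few lines. Item 3 limits it to day 30; the sentence closing item 4 does not. The day limit is hard to put down to loose drafting, because item 4 uses any-time wording for lactate and glucose.

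Renal function is the only one of the three outcomes without an any-time counterpart among the serious adverse events. It is also the one the protocol links most closely to drug risk: Specific study risks says that lactic acidosis on metformin arises mainly with renal impairment, and gives this as the reason for the added safety time point.

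At stake is what the final report can say about renal safety over six months. Under item 3 as written, the designated result describes the first month. Whoever reports the later data must choose between the two definitions after the data exist.

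**Working it through.** The documents give no expected rate, count or power for any safety outcome, so there is no figure of the plan's to reproduce. The check covers the window, what each definition captures, and the share of events the window could leave out.

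**1. The window.** Inputs from Study Intervention and Procedures: 180 days of treatment, full dose from about day 14.
- Share of treatment: 30/180 = 16.7%.
- Share of full-dose days: (30 − 14)/(180 − 14) = 16/166 = 9.6%.

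**2. What is captured after day 30.**

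| Event | Designated outcome (item 3) | Serious adverse event (item 4) | Other |
|---|---|---|---|
| Lactate at or above 2.0 mmol/L | No | Yes, any time | – |
| Fasting glucose below 60 mg/dL | No | Yes, any time | – |
| eGFR below 45 | No | No | Safety event, no day given |

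**3. Share of first eGFR falls after day 30.** Let P be the proportion of an arm that falls below 45 by day 180. P and the timing of falls are not in the documents; the values below are assumptions.

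Constant hazard: P30 = 1 − (1 − P)^(30/180), and the share after day 30 is 1 − P30/P. Expected counts use the planned 25 patients per arm.

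| Assumed P | P30 | Expected by day 30 | Expected by day 180 | Share after day 30 |
|---|---|---|---|---|
| 5% | 0.9% | 0.21 | 1.25 | 83% |
| 10% | 1.7% | 0.44 | 2.5 | 83% |
| 20% | 3.7% | 0.91 | 5.0 | 82% |
| 30% | 5.8% | 1.44 | 7.5 | 81% |

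If only full-dose days carried risk, the exponent becomes 16/166. With P = 10% the share after day 30 is then 90%.

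Front-loaded hazard: if the hazard in the first 30 days is r times the later hazard, P30 = 1 − (1 − P)^(30r/(30r + 150)). With P = 10%:

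| r | 1 | 2 | 3 | 5 | 8 |
|---|---|---|---|---|---|
| Share after day 30 | 83% | 70% | 61% | 49% | 37% |

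The share depends little on P and strongly on the shape of the hazard. The counts assume that every fall is seen. With scheduled draws only at days 30 and 180, a transient dip between them could be missed under either definition.

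**4. Is the late renal sample consistently planned?**
- Item 2 of the monitoring plan: creatinine at day 180.
- Blood tests: a basic metabolic panel at the final visit.
- Table 1: only two marks for the basic metabolic panel, apparently days 0 and 30, and none at day 180.
- Safety Monitoring: renal function at the final visit, but that visit is given as day 90.

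**The case against.** The strongest reply is that nothing is lost. Item 4 makes a GFR below 45 a safety event at any time. The renal action table applies to enrolled patients throughout and provides for a later recheck in some cases. Adverse events are checked at days 30, 180 and 210 in Table 1 and go to the DSMB weekly. Item 3 answers a question about expected toxicities and can be read as describing the one scheduled mid-treatment safety draw, not an analysis window.

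Most of this stands. A reader might infer that a renal decline after day 30 counts nowhere, or is shut out of the safety comparison. The documents support neither. Such a decline is a defined safety event, and no between-arm safety comparison exists for it to be excluded from. Nor does any section say that six-month safety will be claimed from day-30 results.

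The reply does not remove the inconsistency. Item 3 is the only list of designated safety outcomes, and its renal entry names day 30. With no safety analysis specified elsewhere, nothing says which of the two definitions governs reporting.

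**Conclusion.** The point holds as a mismatch in definition, mainly for renal function. The designated renal outcome covers 17% of treatment and about 10% of full-dose days, while the same plan treats the event as a safety event at any time and schedules a day-180 creatinine. For lactate and glucose the day limit matters little, because both are serious adverse events whenever they occur.

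A reader might also infer that most renal events would certainly fall outside the outcome. That is plausible but not shown. It is 81% to 83% under an assumed constant hazard with 5% to 30% affected by day 180, and about half or less if the first-month hazard is five or more times higher. The documents give neither rate nor timing.

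The primary endpoint is unaffected. With 25 patients per arm the renal counts will be small under either window, so the benefit of the fix is complete and unambiguous reporting, not a powered comparison.

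**What to change.** - In item 3, define each of the three outcomes as occurring at any post-baseline measurement: day 30, day 180 or unscheduled.
- State in the Statistical Approach that they will be reported by arm, by visit and cumulatively, with the number of patients measured at each visit. The cumulative count matters because the renal table ends trial participation for some patients, who may then have no day-180 sample.
- Reconcile Table 1 (basic metabolic panel) and Safety Monitoring (final visit at day 90) with Blood tests and item 2, so that the day-180 renal sample is scheduled the same way throughout.
- Do the same for the other two measures. Item 2 does not name glucose, and the final-visit list under Blood tests names neither lactate nor fasting glucose, whereas Table 1 marks both at day 180.

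The cost is a wording amendment plus reconciliation of the schedule. No sample is needed beyond those that some part of the protocol already lists, although a site working from Table 1 alone would have to add the final metabolic panel. No dose or stopping rule needs to change.

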Prospective, single-center, double-blind, randomized placebo controlled trial of 6 months duration, conducted in a tertiary hospital. Patients will be recruited from the General Cardiology Clinics and Center for Advanced Cardiac Care at New York Presbyterian-Columbia Medical Center. This is an extremely busy outpatient heart failure program in which over 2,500 patients are seen yearly. We propose to enroll n=50 patients.

Study Participants: 50 male and female patients will be recruited.

Inclusion Criteria:

- Age >18yrs old
- Patients with chronic heart failure (defined as >6 months duration) uptitrated to recommended or maximally tolerated dose of ACE-I/ARB (unless contraindicated) and beta-blocker (unless contraindicated). If indicated, an aldosterone receptor antagonist should be given (unless contraindicated).

contraindicated). An ICD and/or CRT should be implanted, if indicated. Patients with a CRT device should be treated for > 3 months.

- Reduced ejection fraction defined as LVEF \leq 35%
- NYHA-class II or III with stable symptoms for at least the past 3 months
- Renal Function by eGFR \geq 45 ml/min (MDRD equation) in accordance with FDA guidance on metformin use in CKD(24)
- Non-insulin resistant defined as a fasting insulin resistance index, or HOMA-IR of <2.7.
- Non-diabetic defined as a HgbA1c <6.0

Exclusion Criteria

- Any oral or injectable hypoglycemic therapy (e.g. insulin, sulfonylureas)
- Known allergy to metformin or major side effects to metformin treatment
- Concomitant use of a carbonic anhydrase inhibitor (such as acetazolamide or topiramate)
- Heart Failure Hospitalizations in the past 3 months (primary diagnosis on admission is heart failure)
- Acute myocardial infarction, unstable angina or revascularization with prior 3 months at the time of randomization
- Planned coronary revascularization, heart surgery, CRT implantation or other intervention during the study period that would potentially affect the function of the heart
- Significant, uncorrected primary cardiac valve disease, specifically severely stenotic or regurgitant mitral or aortic valves
- Cardiac arrest or life threatening ventricular arrhythmias within the last 3 months (unless treated with an ICD)
- Atrial fibrillation with poorly controlled ventricular rate at rest (> 110 beats/min)
- Hypertrophic or restrictive cardiomyopathy, infiltrative or storage myocardial disease, active myocarditis, or pericardial disease.

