- Planned major surgery within the study period
- Female patients who are pregnant, nursing, or of childbearing potential while not practicing effective chemical contraceptive methods (i.e. oral, implanted, injectable, or transdermal contraceptive hormones; intrauterine device)
- Current abuse of alcohol or drugs
- Life-expectancy of less than 1 year due to co-existing morbid illness
- Liver disease with ALT or AST >3 times upper normal limit (it is possible to repeat this measurement once within a month)
- Advanced lung disease such as COPD
- Significant comorbidity or issue that makes the patient unsuitable for participation as judged by the investigator

- Participation in another study involving long-term medical intervention (participation in device studies is allowed)

Randomization: After obtaining informed consent, subjects who meet all the inclusion criteria and none of the exclusion criteria will be randomized. Patients will be randomly assigned in a 1:1 ratio to metformin (1000mg twice a day) or placebo treatment groups. The randomization code will be generated by the Columbia University Irving Institution Biostatistics Epidemiology and Research Design Resource (BERD) and held by the Columbia University Medical Center (CUMC) research pharmacy in opaque envelopes prior to the initiation of patient recruitment to ensure allocation concealment. The study drug will be dispensed by the research pharmacy based on randomization assignment. Principal investigator/Co-investigators are responsible to assess the eligibility criteria. Patients and physicians will be blinded to the intervention allocation. Randomization will be performed in block permutations designed by BERD in order to balance the issue of maintaining similarity between treatment groups while simultaneously not employing block sizes which are so small that it is possible to guess some allocations, thus reducing blinding in the trial. A separate randomization table will be generated for those subjects who agree to the PET sub-study (IRB AAR9360). The goal of having two tables is to maintain balanced enrollment between those that do and do not agree to participate in the PET sub-study.

Study Intervention and Procedures

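### Day-0 lactate carries no entry limit or required pre-dose review, and the rise-worded stop rule does not clearly cover a patient already at or above 2.0 mmol/L; screening fasting glucose has a smaller parallel gap

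*Combined protocol and SAP*

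**What the plan says.** **Entry.** The two glycemic criteria under Inclusion Criteria are both upper limits: "Non-insulin resistant defined as a fasting insulin resistance index, or HOMA-IR of <2.7" and "Non-diabetic defined as a HgbA1c <6.0". Patients on glucose-lowering treatment are excluded. No inclusion or exclusion criterion mentions lactate or sets a floor for fasting glucose. The liver-enzyme exclusion does set a numeric limit, and adds that "it is possible to repeat this measurement once within a month".

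**Timing of tests.** Under Blood tests, glucose belongs to screening: "Screening: fasting insulin and glucose level, basic metabolic, liver function test and HgbA1c". Lactate does not: "Baseline: , BNP, venous lactate". Item 2 of the Data and Safety Monitoring Plan lists lactate among the safety tests on days 0, 30 and 180. Table 1 puts lactate, the CPET and study medication allocation in the column headed Screening/Baseline.

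**On-study rules for glucose.** Item 4 of the Data and Safety Monitoring Plan makes it a serious adverse event: "Hypoglycemia: Fasting glucose <60mg/dL, at any point". Table 2 then calls for the current regimen to be discontinued.

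**On-study rules for lactate.** Safety Monitoring counts new lactic acidosis, above 2.0 mmol/L. Item 4 counts a rise, at or above 2 mmol/L. Table 2 acts when lactate rises above 2 mmol/L: study drug is stopped, the medication is to be de-identified (which I read as revealing the allocation), and lactate is repeated daily until normal.

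**The concern.** A marker that stops treatment at a given level should normally be checked against that level before treatment starts. The protocol does this for renal function: entry requires eGFR of at least 45 ml/min, and the dose is reduced from 44 down to 30 and stopped below 30. Lactate and glucose are the other two designated safety outcomes in item 3 of the Data and Safety Monitoring Plan, and neither has an entry counterpart.

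The two markers then fail in different ways. The lactate rule depends on change, so a patient who starts above the level is not clearly covered. The glucose rule is absolute, so a patient who starts below the level is reported and stopped without any change. At stake are a patient starting metformin at the protocol's own stop level, and serious-event reports and drug stops that reflect a usual value rather than a drug effect.

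**Working it through.** The plan states no figure on this point to reproduce. The check is to run two patients through the written rules and then show the scale under stated assumptions.

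**Patient A: lactate 2.2 mmol/L on day 0.** No criterion excludes this patient. The outcome at day 30 depends on how the rise wording is read:

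| Reading of the trigger | Day 30 = 2.2 | Day 30 = 2.3 |
|---|---|---|
| Crossing 2.0 from below | does not fire | does not fire |
| Any increase while at or above 2.0 | does not fire | fires |
| Increase of 2 mmol/L or more (a possible reading of item 4) | does not fire | does not fire; needs 2.2 + 2 = 4.2 |
| Any value above 2.0 | fires, though unchanged | fires |

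Four readings give three different patterns. A value of exactly 2.0 adds another split: it meets item 4 but not Table 2 or Safety Monitoring. If the rule does fire, daily repeats until normal may have no end point for someone whose usual value is 2.2.

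**Patient B: fasting glucose 58 mg/dL at screening and again on day 30.** The inclusion limits are upper limits, so this patient qualifies. On day 30 the value is below 60, so it is a serious adverse event and the regimen is stopped, with a change of 58 - 58 = 0.

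**Scale, lactate.** The documents give no prevalence. Let p be the assumed share at or above 2.0 mmol/L at rest on day 0. Expected patients = 50p; on metformin = 25p; chance of at least one = 1 - (1 - p)^50.

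| p (assumed) | Expected of 50 | On metformin | At least one |
|---|---|---|---|
| 2% | 1.0 | 0.5 | 0.64 |
| 5% | 2.5 | 1.25 | 0.92 |
| 10% | 5.0 | 2.5 | 0.995 |

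**Scale, glucose.** Let q = (assumed share below 60 at screening) x (assumed share of these below 60 again on study). Expected patients = 50q; chance of at least one = 1 - (1 - q)^50.

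- 0.5% x 25%: q = 0.125%, 0.06 patients, chance 6%
- 1% x 25%: q = 0.25%, 0.125 patients, chance 12%
- 1% x 50%: q = 0.5%, 0.25 patients, chance 22%
- 2% x 50%: q = 1%, 0.5 patients, chance 39%

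**Exposure lost to glucose stops.** If every such stop fell on day 30 and were permanent (the protocol does not state permanence), each would lose 150 of 180 days. Planned exposure is 50 x 180 = 9,000 patient-days. The expected loss is 0.0625 x 150/9,000 = 0.1% to 0.5 x 150/9,000 = 0.8% of the trial total.

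**The case against.** The strongest reply is that the plan has backstops. An investigator may exclude a patient for a "Significant comorbidity or issue that makes the patient unsuitable for participation as judged by the investigator". Study drug may be stopped when a patient develops a condition that in the investigator's judgment rules out further therapy. The monitoring board agrees safety measures before the start and reviews adverse events weekly. A clinician seeing 2.2 or 2.3 mmol/L on day 30 might well act. All this is fair, but these provisions permit action without requiring it, name no value for either marker, and the discontinuation provision again depends on something developing on study.

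The second reply is that risk is low. The protocol describes metformin-associated lactic acidosis as lactate above 5 mmol/L, mainly with renal impairment, and controls renal function at entry and on study. This stands: nothing in the documents shows that entering at 2.0-2.3 mmol/L adds harm. What remains is that the protocol itself chose about 2 mmol/L as the level that stops drug.

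The third reply is that the glucose case is hypothetical. Patients on glucose-lowering drugs are excluded, the two earlier trials cited in the Background reported no hypoglycemia, and stopping drug below 60 mg/dL is protective. This also stands, and it makes glucose the lesser part.

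A reader might infer more than the documents support:
- *Lactate goes unchecked before treatment, or dosing precedes the result.* Lactate is measured on day 0 as a safety test. Sharing a Table 1 column with allocation says nothing about order, since consent and HgbA1c sit in the same column and must come first. What is missing is a limit and a required review.
- *Unchanged low glucose will cost substantial treatment time.* That rests on assumed prevalences and on permanent day-30 stops. Glucose is also measured on day 180, when a stop costs nothing, and Table 2 refers to the current regimen rather than naming study drug, although a study-drug stop is the natural reading.
- *The comparison between arms is biased.* Entry values precede treatment, and randomized patients stay in the intention-to-treat analysis.

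**Conclusion.** The point holds as a small, inexpensive correction. Followed exactly, the protocol can start metformin in a patient already at its own lactate stop level, under a trigger that does not clearly apply to that patient. The glucose gap is real on the text but probably rare.

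The lactate part rests on the rise wording, the varying threshold and the absence of any eligibility limit, all of which are in the text. The numbers of patients rest entirely on assumed prevalences (2-10% for lactate; 0.5-2% with 25-50% persistence for glucose), and the documents offer nothing to narrow them. The consequence is limited to patient safety and avoidable serious-event reports and drug stops. There is no effect on bias or on the primary VE/VCO₂ result.

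**What to change.** 1. Before randomization, review the screening fasting glucose and a resting day-0 lactate drawn before the CPET, so that exercise does not produce a false exclusion.
2. Add two eligibility lines: exclude confirmed lactate at or above 2.0 mmol/L and confirmed fasting glucose below 60 mg/dL, with one repeat allowed on the pattern already used for ALT/AST.
3. Use one lactate threshold in Safety Monitoring, in items 3 and 4 of the Data and Safety Monitoring Plan and in Table 2, and name day 0 as the reference for a rise. State that it is a level reached, not an increment of 2 mmol/L.

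The third step belongs with the other two. Once every patient starts below a single threshold, a new event, a rise to the level and a value at the level all describe the same thing, and the daily repeats have a defined end point.

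Both tests are already scheduled. The cost is waiting for the lactate result before allocation, plus a few screen failures: on the assumed 2-10%, the equivalent of 1-5 per 50 otherwise eligible patients, fewer where a repeat clears them. That is a real but modest burden for a single center with narrow criteria.
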